5.3.12. Hematology and biochemistry

For hematology and biochemistry local laboratory will be used. All lab dosages will be done locally.

Any hematology and biochemistry safety sample (Total bilirubin, AST/ALT, Alkaline phosphatase, Lipase INR, Prothrombin, high-sensitivity (hs) Troponin I & T, CPK and NT-proBNP) that does not have a result reported at any visit must be repeated (e.g. if sample is hemolyzed). The sample should be repeated as soon as possible (and recorded as an unscheduled visit in the eCRF).

Each laboratory value that is outside of the institution's normal range will be identified. The investigator will be responsible for assessing the clinical significance of laboratory abnormalities. If the investigator is uncertain about the clinical significance of a laboratory abnormality, he/she will consult with the Sponsor medical monitor. The investigator should follow any clinically significant laboratory abnormalities until resolution.

Table displays the clinical laboratory parameters that must be measured.

Table 2: Laboratory Tests

HEMATOLOGY	BIOCHEMISTRY	STOOLS
Hemoglobin	Sodium	Faecal calprotectin
Hematocrit	Potassium	
WBC	Chloride	
Neutrophils	Calcium	
Lymphocytes	Phosphate	
Monocytes	Glucose	
Eosinophils	BUN or urea	
Basophils	Creatinine	
Platelet count	AST	
ESR	ALT	
Fibrinogen	GLDH	
Prothrombin time and/or INR	Lipase	
	Alkaline phosphatase	
	gGT	
	Total bilirubin	
	Total protein	
	Albumin	
	LDH	
	CRP	
	CPK	
	High-sensitive Troponin T and/or I	
	NT-proBNP	
	Amylase	

The indicative volumes drawn per study visit are presented in the following table.

	COLLECTION TUBE
Hematology (Hemoglobin, Hematocrit, Red Cell Count, MCV, MCHC, Platelets, White cell count with diff.)	2mL EDTA tube
Fibrinogen and Prothrombin Time and/or INR	4,5 mL Na-citrate tube
NT-proBNP	2mL K2 EDTA tube
Biochemistry panel incl CRP, Serum Pregn. and hs Troponin (I and/or T)	3.5mL serum gel tube
miR-124 determination at M12, M36, M48 only	5mL of total blood (PAXgene tube)
ESR	5mL ESR tube

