8.2. Definition of an AESI

The following events will be considered AESI and must be reported to Intuvigilance (same procedure as SAE).

Skin Lesions (regardless of its severity)

A dermatologist consultation should be scheduled to evaluate the type of lesion, its severity and etiology. An anonymized medical report shall be provided.

Headaches

Headaches are frequently reported by patients dosed with ABX464. Abivax follows closely, by means of individual adapted questionnaire, provided in Appendix #4, this AE in specific situations (i.e. headache lasting longer than 72 hours AND not resolved by standard painkillers).

Anemia

Some degree of anemia was found in the 9-month marmoset study with ABX464-N-Glu. Although it has not been reproduced clinically, Abivax performs surveillance for anemia by means of regular determination of hemoglobin and hematocrit levels. Anemia defined as Hb drop > 2 g/dL from baseline or Hb < 8g/dL will be reported as AESI.

Hepatic enzymes

ABX464 showed liver findings in some toxicological studies, hence attention is paid to identification of liver enzymes elevations in subjects. No human predictors of hepatotoxicity for ABX464 or its metabolite, ABX464-N-Glu, have been identified. Based upon preclinical and clinical available data, a DILIsym evaluation of ABX464 was conducted and concluded that there was no risk of DILI in these patients. A signal detection analysis of ALT/AST changes in subjects treated with ABX464 did not reveal any meaningful variation of the mean ALT/AST measurement throughout treatment nor an increased incidence of any liver function tests (LFTs). Sporadic cases of isolated alkaline phosphatase increase have been reported in patients dosed with ABX464.

A specific liver function monitoring plan is implemented in all clinical studies (see Section 5.3.10 and Section 7.2) during the course of treatment and a measurement of LFTs 4 weeks after treatment interruption (during End of Study visit). The LFTs should, as per the clinical protocols, include at least the determination of the liver transaminases (ALT/AST), gamma-glutamyl transferase (GGT), alkaline phosphatase and total bilirubin. Specifically, an increase $\geq 3.0 \times$ ULN in liver transaminases (AST/SGOT and/or ALT/SGPT) or an increase $\geq 2.0 \times$ ULN in total bilirubin without initial findings of cholestasis (elevated alkaline phosphatase) will be reported as AESI.

Severe (grade ≥ 3) infections and opportunistic infections

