Immunosuppression has been observed during the 9-month cynomolgus monkey study with ABX464-N-Glu dosed directly by oral gavage. Therefore, serious (grade 3) infections and opportunistic infections due to bacterial,

mycobacterial, invasive fungal, viral, or parasitic organisms (including aspergillosis, blastomycosis, candidiasis, coccidioidomycosis, histoplasmosis, legionellosis, listeriosis, pneumocystosis, and tuberculosis) will be reported as AESIs. Subjects will be monitored for the development of signs and symptoms of infection during treatment with ABX464. ABX464 will be discontinued if a subject develops a severe (grade 3 or higher) infection, a severe (grade 3 or higher) opportunistic infection, or sepsis.

Acute pancreatic adverse events

Cases of transient increase in lipase serum levels have been observed in ABX464 clinical studies in ulcerative colitis patients as well as in patients with COVID-19 infection (blinded placebo/ABX464 treatment). Therefore, lipase and amylase will be monitored in the clinical studies. An elevation of serum lipase and/or amylase at least three times greater than the upper limit of normal will be reported as AESI and a workup for a diagnosis of pancreatitis will be performed according to the Atlanta criteria for the definition of acute pancreatitis.

Definition of diagnosis of acute pancreatitis^[10]

The diagnosis of acute pancreatitis requires two of the following three features:

- Abdominal pain consistent with acute pancreatitis (acute onset of a persistent, severe, epigastric pain often radiating to the back);
- Serum lipase activity (or amylase activity) at least three times greater than the upper limit of normal; and
- Characteristic findings of acute pancreatitis on contrast-enhanced computed tomography (CECT) and less commonly magnetic resonance imaging or transabdominal ultrasonography.

If abdominal pain suggests strongly that acute pancreatitis is present, but the serum amylase and/or lipase activity is less than three times the upper limit of normal, as may be the case with delayed presentation, imaging will be required to confirm the diagnosis. The CECT will be planned and performed locally in that case.

If the diagnosis of acute pancreatitis is established by abdominal pain and by increases in the serum pancreatic enzyme activities, a CECT is not usually required for diagnosis in the emergency room or on admission to the hospital.

Malignancies including Non-Melanoma Skin Cancers

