8.4. Events or Outcomes Qualifying as AEs or SAEs

8.4.1. Clinical laboratory parameters

Abnormal laboratory findings (e.g., clinical chemistry, hematology) or other abnormal assessments (e.g. vital signs) that are judged by the investigator as **clinically significant** will be recorded as AEs or SAEs if they meet the definitions of sections 8.1 and 8.2 respectively. Clinically significant abnormal laboratory findings or other abnormal assessments that are detected during the study or are present at informed consent and significantly worsen during the study will be reported as AEs or SAEs. Clinically significant abnormal laboratory findings or other abnormal assessments that are associated with the disease being studied, and are present at the start of the study but do not worsen, will **not** be reported as AEs or SAEs. However, if these findings or assessments are judged by the investigator to be more severe than expected considering the subject's condition, then they may be reported as AEs or SAEs.

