### 9.2 EXTERNAL DATA

#### 9.2.1 Laboratory Data

For hematology and biochemistry local laboratory are used. All lab dosages are done locally.

The following clinical laboratory parameters are measured:

*Hematology:* Hemoglobin, Hematocrit, White Blood Cell (WBC), Neutrophils, Lymphocytes, Monocytes, Eosinophils, Basophils, Platelet count, ESR, Fibrinogen, Prothrombin time and/or INR.

*Biochemistry:* Sodium, Potassium, Chloride, Calcium, Phosphate, Glucose, Blood Urea Nitrogen (BUN) or urea, Creatinine, Aspartate Transaminase (AST), Alanine Transaminase (ALT), Glutamate Dehydrogenase (GLDH), Lipase, Alkaline phosphatase, gamma-Glutamyl Transferase (gGT), Total bilirubin, Total protein, Albumin, Lactate Dehydrogenase (LDH), C-reactive protein (CRP), Creatine Phosphokinase (CPK), High-sensitive Troponin T and/or I, N-terminal pro-brain natriuretic peptide (NT-proBNP), Amylase.

*Stools:* Faecal calprotectin.

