##### **Adverse Events of Special Interest (AESI):**

The following events will be considered as AESIs:

- Skin Lesions (regardless of its severity)
- Headaches (if lasts more than 72 hours AND is not resolved by standard painkillers)
- Anemia (Hemoglobin drop  $> 2$  g/dL from baseline or Hemoglobin  $< 8$  g/dL)
- Hepatic enzymes (specifically, an increase  $\geq 3.0 \times$  ULN in liver transaminases (AST/SGOT and/or ALT/SGPT) or an increase  $\geq 2.0 \times$  ULN in total bilirubin without initial findings of cholestasis (elevated alkaline phosphatase))
- Severe (grade  $\geq 3$ ) infections and opportunistic infections
- Acute pancreatic adverse events (an elevation of serum lipase and/or amylase at least three times greater than the upper limit of normal will be reported as AESI)
- Malignancies including Non-Melanoma Skin Cancers
- Cardiac AESIs: any AE with the SOC “cardiac disorders” (Aortic valve disease, Asystole, Atrial fibrillation, Atrial flutter, 3rd degree AV block (AV block complete), Cardiac arrest, Chest pain – cardiac, Heart failure, Left ventricular systolic dysfunction, Mitral valve disease, Mobitz (type) II atrioventricular block (type 2, 2nd degree AV block), Myocardial infarction, Myocarditis, Pericardial effusion, Pericardial tamponade, Pericarditis, Pulmonary valve disease, Restrictive cardiomyopathy, Right ventricular dysfunction, Sick sinus syndrome, Tricuspid valve disease, Ventricular fibrillation, Ventricular tachycardia).

Further definitions for the AESIs are described in protocol section 8.2.

Two periods will be defined for TEAE:

- Any adverse event which occurs or worsens from first dosing (BOLS) to the last dosing day;
- Any adverse event which occurs after the last dosing day.

Adverse events will be described by primary system organ class and preferred term. Numbers and percentage of subjects, and number of occurrences of adverse event will be presented for:

- AE (*Table 14.3.1.1*);
- AE by severity (*Table 14.3.1.2*);
- TEAE by relationship to study drug (*Table 14.3.1.3*);
- TEAE leading to investigational product discontinuation (*Table 14.3.1.4*);
- TEAE (*Table 14.3.1.5*);
- TEAE by severity (*Table 14.3.1.6*);
- Severe TEAE (grade 3 or 4) by relationship to study drug (*Table 14.3.1.7*);
- Serious TEAE (*Table 14.3.1.8*);
- TEAE of special interest (*Table 14.3.1.9*);

All adverse events will be listed and the data will be tabulated by body system/organ class (N and percentage).

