### 11.6.2 Laboratory Data

The absolute values of each laboratory parameter (Hematology, Biochemistry) will be summarised at each visit along with the change from baseline to each post baseline timepoint (*Table 14.3.3.1 and 14.3.3.2*). In addition, shift tables from baseline to each post baseline timepoint will be presented (*Table 14.3.3.3 and 14.3.3.4*) to show Normal/ Abnormal Clinically Significant (CS)/ Abnormal Not Clinically Significant (NCS) results.

Laboratory data listings will be presented in two ways:

- Abnormal values (presented within the data summaries) (*Table 14.3.3.5*)

- All laboratory data (presented within the data listings)

If lab results are repeated at the same visit, the repeated result will be used in summaries (instead of the original one) provided the sample was taken within the visit window, otherwise the original result will be used. All results will be listed.

Lab results at unscheduled visits will be included in the listings but will not be summarised.

Serum pregnancy data will be listed only.

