## Listing 16.2.8.1 Laboratory Measurements: Hematology

| Parameter | Treatment | Centre/
Patient
number | Visit     | Was sample
taken? | Result | Unit | Range           | Investigator's interpretation     |
|-----------|-----------|------------------------------|-----------|----------------------|--------|------|-----------------|-----------------------------------|
| Parameter | xxxxxx    | xxxx-xxx                     | Screening | Yes/ No (reason)     | xxx.xx | xxxx | xxx.xx - xxx.xx | Normal/ Abnormal CS/ Abnormal NCS |
|           |           |                              | Visit     | Yes/ No (reason)     | xxx.xx | xxxx | xxx.xx - xxx.xx | Normal/ Abnormal CS/ Abnormal NCS |
|           |           |                              | Visit*    | Yes/ No (reason)     | xxx.xx | xxxx | xxx.xx - xxx.xx | Normal/ Abnormal CS/ Abnormal NCS |
|           |           |                              | Etc       |                      |        |      |                 |                                   |
|           |           | xxxx-xxx                     | Screening |                      | xxx.xx | xxxx | xxx.xx - xxx.xx | Normal/ Abnormal CS/ Abnormal NCS |
|           |           |                              | Etc       |                      |        |      |                 |                                   |
|           |           |                              | Etc       |                      |        |      |                 |                                   |
|           | Etc       |                              |           |                      |        |      |                 |                                   |

\*Outside the visit window

CS=Clinically Significant; NCS=Not Clinically Significant

Path\filename

Page x/y

Programming Note: Please include “\*Outside the visit window” footnote if applicable.

For the Treatment column, please present treatment for ABX101 + ABX102 study consistently to the table headers.

This layout also applies to:

Listing 16.2.8.2 Laboratory Measurements: Biochemistry

Version Date 20 MAY 2021

Template STATt004

Page 89 of 97

ABX464-102

ddMMMyyyy HH:MM

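### Laboratory-defined AESIs are counted only where the site recorded an adverse event; no planned table counts threshold breaches from the measured values, and the shift tables show neither direction nor size.

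*SAP*

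**What the plan says.** **AESI rules.** Protocol 8.2 sets measured-value triggers:

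- Hemoglobin: "Anemia defined as Hb drop > 2 g/dL from baseline or Hb < 8g/dL will be reported as AESI".
- Liver: ALT or AST at or above 3 × ULN, or total bilirubin at or above 2 × ULN without initial cholestasis.
- Pancreas: "An elevation of serum lipase and/or amylase at least three times greater than the upper limit of normal will be reported as AESI".
- Cardiac laboratory parameters: a relative change above 20% from baseline.

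SAP 11.6.1 repeats the first three groups. It covers the cardiac laboratory rule only by referring back to protocol 8.2.

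**General recording rule.** Protocol 8.4.1 ties the recording of laboratory findings as AEs or SAEs to clinical significance. It speaks of "Clinically significant abnormal laboratory findings or other abnormal assessments that are detected during the study". Protocol 5.3.12 says who decides: "The investigator will be responsible for assessing the clinical significance of laboratory abnormalities".

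**AESI count.** SAP 11.6.1 states "Numbers and percentage of subjects, and number of occurrences of adverse event will be presented for" a list of event types that includes TEAEs of special interest (Table 14.3.1.9). That table takes the layout of Table 14.3.1.1, whose source is AE Listing 16.2.7.

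**Laboratory outputs.** SAP 11.6.2 plans values and changes by visit (Tables 14.3.3.1 and 14.3.3.2), shift tables (14.3.3.3 and 14.3.3.4) "to show Normal/ Abnormal Clinically Significant (CS)/ Abnormal Not Clinically Significant (NCS) results", and a listing of abnormal values (14.3.3.5). The shift categories come from the column headed "Investigator's interpretation" in Listings 16.2.8.1 and 16.2.8.2. Results from unscheduled visits are listed but not summarised.

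**The concern.** Long-term safety is the primary objective. The number of treatment-emergent AESIs and the number of specific laboratory abnormalities are both named secondary endpoints (protocol 2.4, SAP 4.2). A laboratory AESI is the kind of event that can be verified from the database, because the result, its unit and the local reference range are all held. As planned, a breach that the site does not enter as an AE is missing from Table 14.3.1.9, and no other table counts it.

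The shift tables do not act as a check. They group every abnormal result by the investigator's opinion of it, so a small and a large rise, or a fall and a rise, can share one cell.

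**Working it through.** There is no planned sample size, power or event figure to reproduce. The check traces each output to its source and then gives the scale.

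**1. AESI table.** Table 14.3.1.9 leads to Listing 16.2.7, which holds recorded adverse events and has no AESI column. No SAP section derives an 8.2 breach from Listings 16.2.8.1 or 16.2.8.2.

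**2. The two protocol rules.** The 8.2 triggers carry no significance test, while 8.4.1 is built on one. Neither section says how they fit together. Section 8.4.1 also cites 8.2 as though it were the SAE definition, which stands in 8.3.

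**3. Shift tables.** Illustration, assuming an ALT ULN of 40 U/L:

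- 30 to 45 U/L: 45/40 = 1.1 × ULN, below the 3 × ULN trigger.
- 30 to 130 U/L: 130/40 = 3.25 × ULN, above it.

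If both are marked NCS, both read Normal to Abnormal NCS. Hemoglobin 14.0 to 11.8 g/dL (a drop of 2.2, which meets the rule) and 14.0 to 18.0 g/dL (which does not) also share a cell if both are abnormal and marked NCS. If the local lower limit is 11.8 g/dL or less, the first stays Normal to Normal and does not reach the abnormal-value listing either. Entry allows ALT up to just under 1.5 × ULN, so a move from 1.2 to 4.9 × ULN can stay within Abnormal NCS.

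**4. Do other outputs supply the count?**

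- Tables 14.3.3.1 and 14.3.3.2 pool values from local laboratories with their own ranges. A pooled maximum cannot be read as a multiple of ULN.
- Protocol 7.2 calls for twice-weekly liver retests after a rise of 3 × ULN or more. Retest peaks may fall at unscheduled visits, which are not summarised. A repeat within the visit window replaces the original value.
- Table 14.3.3.5 is a listing, not a subject count.
- Protocol 9.3 promises, for each parameter, the number of subjects with at least one abnormal value. The SAP shells give per-visit rows only, and SAP 1.2 does not declare a change.
- The endpoint on specific laboratory abnormalities has neither a definition of which abnormalities are meant nor a count table in SAP 14.1.

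**5. Scale.** N = 22 enrolled (15 previously on ABX464, 7 on placebo; protocol 1.3), assuming all were dosed. One subject is 1/22 = 4.5 points in the total column, 1/15 = 6.7 and 1/7 = 14.3 points in the group columns. Exact (Clopper-Pearson) 95% intervals for the total:

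| Subjects | Incidence | 95% CI |
|---|---|---|
| 0/22 | 0% | 0 to 15.4% |
| 1/22 | 4.5% | 0.1 to 22.8% |
| 2/22 | 9.1% | 1.1 to 29.2% |

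**6. Chance of a missed subject.** Let k be the number of subjects with a true breach and u the chance that a breach is not recorded (independent between subjects). P(at least one uncounted) = 1 − (1 − u)^k. The documents give no u, so these values are assumptions:

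| k | u = 10% | u = 25% | u = 50% |
|---|---|---|---|
| 2 | 19% | 44% | 75% |
| 4 | 34% | 68% | 94% |

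**The case against.** The strongest reply is that protocol 8.2 already settles the matter. Its triggers are numeric and mandatory, and they follow the SAE route with a 24-hour deadline. The AE definition in 8.1 includes an abnormal laboratory finding without a significance test, and 8.4.1 does not mention AESIs. This stands against a reading that a reader might infer: that the AESI count follows the CS/NCS flag, so that a breach judged not significant is excluded by rule. The documents do not say so. The count depends on whether the site records the event.

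Safeguards also exist: out-of-range checks at data entry (protocol 11.2), source verification (11.4) and review of key listings before lock (SAP 9.5). They lower the risk, but none is described as a check against the 8.2 thresholds.

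Second, direction and size are not lost from the report. Tables 14.3.3.1 and 14.3.3.2 and the abnormal-value listing retain them, and with 22 subjects a listing can be read by eye. That limits the damage but does not produce the endpoint. Nor is it right that a trend in a subject already abnormal at entry can never show, because a change from NCS to CS would.

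Third, the SAP follows the protocol, which bases potentially clinically significant abnormalities on investigator judgement (9.3). That is a reason to keep the CS/NCS flag, not a reason to omit a threshold count.

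Finally, SAP 9.2.1 names "High-sensitive Troponin T and/or I" as one item, and likewise BUN or urea. A reader might infer that different assays are averaged together. That section lists what is measured and does not say how it is summarised, so the inference is unsupported and forms no part of this point.

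**Conclusion.** The point holds as a gap in the outputs. Laboratory AESIs are mandatory threshold reports, but their count rests on site recording alone. The measured values that could verify it are not used, and two promised counts (the secondary endpoint on specific laboratory abnormalities and the protocol 9.3 count of subjects with an abnormal value) have no table. The shift tables cannot fill the gap, because they carry only the investigator's call.

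Each unrecorded subject is worth 4.5 points in the total column, and at 0 against 1 subject this decides whether a signal appears at all. How many subjects would be missed is unknown: no missed breach is shown, and the probabilities above rest on assumed rates. This is an inexpensive improvement that should be made, not evidence that the reported safety counts will be wrong.

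**What to change.** 1. **Add a threshold table.** From all scheduled, repeat and unscheduled post-baseline results, give the number (%) of subjects meeting each existing protocol 8.2 laboratory criterion: hemoglobin, ALT/AST, bilirubin (derived together with alkaline phosphatase, because of the cholestasis condition), lipase/amylase, and the 20% change rule for cardiac laboratory parameters. Use the SAP's two TEAE periods so that it lines up with Table 14.3.1.9, print it beside the reported AESIs, and reconcile differences before lock. State which abnormalities make up the secondary endpoint. For NT-proBNP, state the reference value: the flow chart schedules it only at M42, M48 and end of study, so a value before the first dose may not exist.
2. **Rebuild the shift tables.** Use Low/Normal/High against the local range, with × ULN classes for liver and pancreatic enzymes, and add the worst on-treatment value. Add the protocol 9.3 count of subjects with at least one abnormal value. Keep CS/NCS as a flag. Correct the visit rows of the Table 14.3.3.3 shell, which print Abnormal CS twice and omit Abnormal NCS.
3. **Reconcile the text.** State that protocol 8.2 governs AESI reporting regardless of the significance test in 8.4.1, and write the cardiac laboratory rule into the SAP list.

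No threshold changes and no new data are needed, since results, units and local ranges are already collected. The cost is programming, some site queries and possibly late AESI reports before lock. The AESI count may rise.

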7.2. Study discontinuation criteria

Subjects who are not found eligible or not willing to enter the ABX464-108 study are not considered as prematurely discontinued as they have completed the scheduled treatment of ABX464-102 study.

A subject can be withdrawn at any time from the study for the following reasons:

Subject's study discontinuation could occur for the following reasons:

- Investigator's decision;
- An Adverse Event or an intercurrent condition that preclude continuation of treatment;
 - specifically, an increase $\geq 3.0 \times$ ULN in liver transaminases (AST/SGOT and/or ALT/SGPT) or an increase $\geq 2.0 \times$ ULN in Alkaline phosphatase or in total bilirubin requires close observation with repeating liver enzymes and serum bilirubin tests two times weekly and clinical investigation to understand the etiology of this elevation. Frequency of retesting can decrease to once a month if abnormality stabilizes after the initial two weeks of follow-up and if the patient is asymptomatic. Discontinuation of the study treatment should occur if:
 - ALT or AST $> 8 \times$ ULN
 - ALT or AST $> 5 \times$ ULN for more than 2 weeks
 - ALT or AST $> 3 \times$ ULN and total bilirubin $> 2 \times$ ULN or INR > 1.5
 - ALT or AST $> 3 \times$ ULN with appearance of fatigue, nausea, vomiting, right upper quadrant pain or tenderness, fever, rash, and/or eosinophilia ($> 5\%$);
 - Severe (grade 3 or higher) infection, a severe (grade 3 or higher) opportunistic infection, or sepsis;
 - Any cardiac AESI or condition diagnosed during the course of the study and assessed by the clinical adjudication committee as changing the risk/benefit balance for the subject;
 - New onset of acute pancreatitis;
 - Malignancies (including non-melanoma skin cancers);
 - Any relevant toxicity or negative change in the risk/benefit assessment leading to an unacceptable risk for the subject or any data deriving from other clinical trials or toxicological studies which negatively influence the risk/benefit assessment. This may be applicable but is not limited to the following cases: occurrence of AEs which character, severity or frequency is new in comparison to the existing risk profile, or clinically significant abnormal laboratory results, including new onset anemia (defined as a hemoglobin decrease > 2 g/dL from baseline or hemoglobin < 8 g/dL

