If changes in severity for the same Treatment Emergent Adverse Event (TEAE) have been reported separately but with the same adverse event (AE) number, they will be collapsed to a single AE with maximum severity for the summary tables but listed as reported.

Classifications of medical history, concomitant medication and adverse events will be sorted alphabetically within the summary tables.

If any laboratory assessments are repeated at the same visit, the result from the repeat assessment will be used in summaries. Both values will be listed.

Data collected on the eCRF will be presented within data listings. The data listings will be sorted by treatment group, patient number and visit. Visits outside the visit windows will be identified within the listings.

The date format for all output presentations will be 'ddMMMyyyy'.

All statistical analysis will be performed using SAS ® Enterprise Guide V 8.3 or higher.

If any of the assumptions underlying the formal statistical methods proposed are violated during the analysis of the final data, alternative statistical methods will be used and any changes documented in the statistical methods section of the CSR, including the rationale for use.

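### SAP 10.1 and 11.6.2 conflict on repeated laboratory tests, and both let a same-visit repeat replace a valid result, so the abnormal-value count in Protocol 9.3 is not assured

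*SAP*

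**What the plan says.** Two SAP sections govern repeats. SAP 10.1: "If any laboratory assessments are repeated at the same visit, the result from the repeat assessment will be used in summaries". SAP 11.6.2 opens in the same way: "If lab results are repeated at the same visit, the repeated result will be used in summaries (instead of the original one"). It then attaches a condition to the replacement, which SAP 10.1 lacks: the repeat counts only if it was drawn inside the visit window, and if not, the first value stands. Both values are listed either way. On other retests SAP 11.6.2 adds: "Lab results at unscheduled visits will be included in the listings but will not be summarised".

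The protocol gives two reasons to repeat a safety test.

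- Protocol 5.3.12 covers a safety sample "that does not have a result reported at any visit must be repeated", for example after haemolysis. The repeat goes into the eCRF as an unscheduled visit.
- Protocol 7.2 covers raised liver tests. A rise past the stated limits "requires close observation with repeating liver enzymes and serum bilirubin tests two times weekly".

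Protocol 9.3 wants the shift tables to give, for each parameter, how many subjects had at least one abnormal value. SAP 11.6.2 plans shift tables from baseline to each later timepoint, in the categories Normal, Abnormal CS and Abnormal NCS. SAP 1.2 lists no departure from the protocol on this point.

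**The concern.** Long-term safety is the primary objective, and the number of specific laboratory abnormalities is a secondary endpoint. A repeat rule is harmless if it only fills in for samples that failed. This one has no such limit, and it may act the wrong way round. After a failed sample there is nothing to overwrite, and the repeat that should stand in is kept out of the summaries as unscheduled. Where a valid result exists, a common reason to test again is that it was abnormal. Keeping the second draw in those cases is regression to the mean by rule: any error it introduces in the aggregate tables leans towards normal. The listings keep the first value, but they do not count subjects.

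**Working it through.** The plan gives no figure on this point, so there is none to reproduce. The check sets the rules side by side and then bounds the effect.

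**1. What each rule does**

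| Situation | SAP 10.1 | SAP 11.6.2 |
|---|---|---|
| Valid first result, same-visit repeat inside the window | repeat summarised | repeat summarised |
| Valid first result, same-visit repeat outside the window | repeat summarised | first result summarised |
| Valid first result, retest entered as unscheduled | not addressed | first result summarised, retest listed only |
| Failed sample, repeat entered as unscheduled (Protocol 5.3.12) | not addressed | no value summarised, repeat listed only |

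Row 2 is the conflict. Row 1 is where a valid abnormal value can be lost. Row 4 is where a legitimate substitute is lost.

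**2. Whether the window condition protects the first result**

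Inputs: windows of ±2, ±4 and ±14 days (Protocol 5.1 flow chart, SAP 3.4); twice weekly taken as every 3.5 days. The retests that fit are the whole number of 3.5-day steps left in the window.

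| Window | First draw on the nominal day | First draw at window start |
|---|---|---|
| ±2 days | 2/3.5, so 0 | 4/3.5, so 1 |
| ±4 days | 4/3.5, so 1 | 8/3.5, so 2 |
| ±14 days (after M24) | 14/3.5 = 4 | 28/3.5 = 8 |

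After M24 the window is a weak filter, but only if retests are entered under the scheduled visit. Eight retests would also need twice-weekly testing to last four weeks, whereas Protocol 7.2 lets it fall to monthly after two weeks if the abnormality is stable and the patient has no symptoms.

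**3. Possible effect on a count**

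Expected abnormal count summarised = x(1 − rq). Here x is the number of abnormal first results, r the share repeated at the same visit and in window, and q the share of those repeats that are normal. Subjects enrolled: 22 (Protocol 1.3), so one subject is 1/22 = 4.5%. The documents give none of x, r or q; all are assumed.

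| x | r = 0 | r = 0.5, q = 0.3 to 0.7 | r = 1, q = 0.3 to 0.7 |
|---|---|---|---|
| 2 (9.1%) | 2.0 (9.1%) | 1.7 to 1.3 (7.7% to 5.9%) | 1.4 to 0.6 (6.4% to 2.7%) |
| 4 (18.2%) | 4.0 (18.2%) | 3.4 to 2.6 (15.5% to 11.8%) | 2.8 to 1.2 (12.7% to 5.5%) |

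If retests are always entered as unscheduled, r = 0 and nothing is lost.

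**4. How far one repeat moves a raised ALT**

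Assumption: independent lognormal variation within a patient whose true level is unchanged, CV 15% to 30%. P(repeat < c × ULN) = Φ(ln(c/true)/s), with s = √ln(1 + CV²), which is 0.149 at 15% and 0.294 at 30%.

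- True level 2.5 × ULN, c = 3: Φ(0.182/0.149) = 0.889 and Φ(0.182/0.294) = 0.733.
- True level 3.0, c = 3: 0.5. True level 3.5, c = 3: 0.151 and 0.300.
- True level 2.5, c = 1 (back to normal): Φ(−0.916/0.294) = 0.0009 at CV 30%, effectively zero at 15%.
- True level 1.0, c = 1: 0.5.

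So a repeat often crosses back under 3 × ULN but almost never moves a clearly raised ALT to Normal. Values of q such as 0.3 to 0.7 are plausible only for results near the limit of normal.

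**The case against.** The strongest reply is that the rule rarely bites. Liver retests taken days apart are naturally unscheduled visits. Protocol 5.3.12 records even the repeat of a failed sample that way, and SAP 11.6.2 keeps unscheduled results out of the summaries, so they displace nothing. Where several visits fall in one window, SAP 3.4 takes the one nearest the scheduled time, which selects on timing and not on value. Abnormal first results remain visible in Table 14.3.3.5 ("Abnormal values (presented within the data summaries"). ALT or AST at or above 3 × ULN, and the haemoglobin, bilirubin, lipase and amylase thresholds, are AESIs in their own right (Protocol 8.2, SAP 11.6.1). Clinically significant abnormalities are recorded as adverse events (Protocol 8.4.1). A reported result may also be technically suspect, so some same-visit replacements are proper.

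Most of this stands, and it rules out stronger readings. A reader might infer that any repeat displaces the first value. It does not: the repeat must be at the same visit and, under SAP 11.6.2, in window. A reader might also take the 73% to 89% in step 4 as the chance that an abnormal result disappears from the shift tables. It is the chance of falling below 3 × ULN, where the result is still abnormal.

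The reply does not settle two things. No text says that liver retests must be entered as unscheduled. And nothing limits same-visit replacement to results that were invalid.

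**Conclusion.** The point holds in a limited form. The two SAP rules conflict for a same-visit repeat drawn outside the window. Both allow a valid abnormal result to be overwritten in by-visit summaries and shift tables, and a repeat after a failed sample is left out. By-visit shift tables built this way cannot guarantee the Protocol 9.3 count.

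The size is unknown and probably small. It depends on how sites enter retests, which the documents do not say, and it is zero if all are unscheduled. Results near the limit of normal are the most exposed. Larger liver, haemoglobin and pancreatic abnormalities are captured as AESIs. The documents do not support saying that safety signals are selectively removed: such a loss is possible under the rule, not planned, and every result is listed. In a descriptive, open-label study of 22 subjects this is a minor clarification, worth considering before database lock.

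**What to change.** - **One rule in SAP 10.1 and 11.6.2.** Post-baseline by-visit summaries use the first result if it is valid. A repeat, including one recorded as unscheduled under Protocol 5.3.12, replaces it only when the first gave no reportable result or was documented as technically invalid. Baseline keeps its own definition in SAP 5.1.
- **Add the Protocol 9.3 count.** The shift tables should show, for each parameter, the number and percentage of subjects with at least one abnormal post-baseline value, counting all valid results including unscheduled ones. That count does not depend on which value is chosen for a visit.

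The cost is a few sentences of SAP text and minor programming, with no new data. Laboratory tables may look slightly less favourable. The any-abnormal count will also rise with the number of tests a subject has, so a footnote should say that unscheduled results are included.
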